### **3.8. Analysis Visit Windows**

#### **3.8.1. Definition of Study Day**

Study day will be calculated from the first dose date of any study drug and derived as follows:

- For postdose study days: Assessment Date – First Dose Date of Any Study Drug + 1
- For days prior to the first dose: Assessment Date – First Dose Date of Any Study Drug

Therefore, study Day 1 is the day of first dose of study drug administration.

The last dose date of an individual study drug will be the stop date on the study drug administration eCRF for the record where the “study drug was permanently withdrawn” flag is “Yes”.

If the last study drug dosing date is missing, the latest date among the study drug end date, clinical visit date, laboratory sample collection date, and vital signs assessment date that occurred during the on-treatment period will be used.

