### **1.3. Sample Size and Power**

Due to the exploratory nature of this study, the sample size was not determined by any formal power calculation. The number of subjects in each treatment group was decided based on clinical experience.

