#### **3.8.2. Analysis Visit Windows**

Subject visits might not occur on protocol-specified days. Therefore, for the purpose of analysis, observations will be assigned to analysis windows.

- For Groups 1-3 and 5

Data collected up to 3 days after the last dose date of GS-9992 or TAF, whichever comes last, will be considered as on-treatment data whereas data collected afterwards will be considered as posttreatment data.

- For Group 4

Data collected up to 3 days after the last dose date of GS-9992 or 3 days after the subjects have discontinued commercially available NUC(s), whichever comes last, will be considered as on-treatment data whereas data collected afterwards will be considered as posttreatment data.

On-treatment data will be mapped to the analysis windows defined in [Table 3-1](#), [Table 3-2](#), [Table 3-3](#) and [Table 3-4](#).

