### **4.2.1. Duration of Exposure to Study Drug**

Total duration of exposure to study drug will be defined as last dose date minus first dose date plus 1, regardless of any temporary interruptions in study drug administration, and will be expressed in weeks using up to 1 decimal place (eg, 4.5 weeks). If the last study drug dose date is missing, the latest date among the study drug end date, clinical visit date, laboratory sample collection date, and vital signs assessment date that occurred during the on-treatment period will be used.

The total duration of exposure to GS-9992 and TAF will be summarized using descriptive statistics (n, mean, SD, median, Q1, Q3, minimum, and maximum) and using the number (ie, cumulative counts) and percentage of subjects exposed through the following time periods: Baseline, Week 1, Week 2, Week 4, Week 8, Week 12 for both GS-9992 and TAF, and additionally Week 16, Week 20, Week 24, Week 28, Week 32, Week 36, Week 40, Week 44 and Week 48 for TAF.

A 3-day window is applied to the last planned on-treatment visit to match with the protocol-specified visit window. Summaries will be provided for each treatment group for the Safety Analysis Set.

No formal statistical testing is planned.

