## 7.1.5. Treatment-Emergent Adverse Events

### 7.1.5.1. Definition of Treatment-Emergent Adverse Events

For the **Analysis for 12 Week Regimen**, treatment-emergent adverse events (TEAEs) are defined as follows:

- For subjects treated with GS-9992 and TAF or commercially available NUC(s) (ie, Group 1, 3, 4 and 5):

Any AEs with an onset date on or after the first dose date of any study drug and no later than 30 days after permanent discontinuation of GS-9992

Any AEs leading to premature discontinuation of any study drug during the first 12 weeks (ie, from Day 1 to Day 84).

- For subjects treated with TAF only (ie, Group 2):

For those who remained on TAF treatment for the first 12 weeks plus 30 days (ie, from Day 1 to Day 114):

- Any AEs with an onset date on or after the first dose of TAF and no later than 30 days after the first 12 weeks treatment of TAF (ie, no later than Day 114)

For those who prematurely discontinued TAF during the first 12 weeks plus 30 days (ie, from Day 1 to Day 114):

- Any AEs with an onset date on or after the first dose of TAF and no later than 3 days after permanent discontinuation of TAF or up to Day 114, whichever comes earlier
- Any AEs leading to premature discontinuation of TAF

For the **Analysis for 48 Week Regimen**, TEAEs are defined as follows:

- For subjects treated with GS-9992 and TAF (ie, Group 1, 3 and 5):

Any AEs with an onset date on or after the first dose date of any study drug and no later than 3 days after permanent discontinuation of TAF or 30 days after permanent discontinuation of GS-9992, whichever comes last

Any AEs leading to premature discontinuation of any study drug during the 48 weeks treatment

- For subjects treated with TAF only (ie, Group 2):

Any AEs with an onset date on or after the first dose date of TAF and no later than 3 days after permanent discontinuation of TAF

Any AEs leading to premature discontinuation of TAF during the 48 weeks treatment

- Subjects treated with GS-9992 and commercially available NUC(s) (ie, Group 4) are not included in treatment-emergent **Analysis for 48 Week Regimen**.

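### A missing GS-9992 stop date could be imputed as late as Week 48, because the fallback uses an on-treatment period that lasts until TAF or the NUC also ends

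*SAP*

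**What the plan says.** SAP 3.8.1 works drug by drug: "The last dose date of an individual study drug will be the stop date on the study drug administration eCRF", read from the record on which permanent withdrawal is marked Yes. If that date is absent, a fallback applies: "If the last study drug dosing date is missing, the latest date among the study drug end date, clinical visit date, laboratory sample collection date". The sentence closes with the words "vital signs assessment date that occurred during the on-treatment period will be used". Nothing ties the fallback to the drug whose date is missing. Section 4.2.1, which summarises exposure to GS-9992 and to TAF, repeats it: "If the last study drug dose date is missing, the latest date among the study drug end date, clinical visit date, laboratory sample collection date".

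The SAP says what counts as on-treatment only in 3.8.2. In the viremic groups (1, 2, 3 and 5) the rule is: "Data collected up to 3 days after the last dose date of GS-9992 or TAF, whichever comes last, will be considered as on-treatment data". For Group 4 the last GS-9992 dose is set against the end of the NUC: "3 days after the subjects have discontinued commercially available NUC(s), whichever comes last, will be considered as on-treatment data".

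In the 12 Week Regimen analysis for Groups 1 and 3-5, the end of GS-9992 fixes three things: the data cut (SAP 2.1.1), the laboratory-abnormality window (7.2.3.1) and the treatment-emergent AE window. The AE definition (7.1.5.1) begins "Any AEs with an onset date on or after the first dose date of any study drug and no later than 30 days after permanent" and goes on to name the stopping of GS-9992 as the event from which the 30 days run. None of these has a calendar limit. In Group 2 the AE and laboratory windows go no later than Day 114.

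**The concern.** By design, every GS-9992 group stops GS-9992 at Week 12 and continues TAF or a NUC to Week 48 (Protocol 3.4). A period that closes with the longer drug is the wrong place to look for the end of the shorter one. Read literally, the fallback moves a missing GS-9992 stop date to the last visit on TAF or NUC.

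The safety of the 12-week regimens is a primary objective, and Protocol 8.6 anchors the primary safety analysis to the last GS-9992 dose. Events and laboratory abnormalities from the 36 weeks without GS-9992 could enter the 12-week tables. Because Group 2 is capped, the window can lengthen only in the GS-9992 groups. Group 4 is left out of the 48-week treatment-emergent analysis, yet its late data could enter the 12-week tables by this route.

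The date need not be blank. It is recognised only from a flagged record, and the fallback takes the latest of several dates. A GS-9992 end date on an unflagged record would therefore lose to any later visit. A subject who stopped GS-9992 early, with the date unrecovered, could be counted as exposed through Week 12.

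**Working it through.** This is date arithmetic; no sample-size formula is involved.

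**Inputs**
- GS-9992 for 12 weeks, TAF or NUC to Week 48 (Protocol 3.4).
- Week 48 is nominal Day 337 and Week 12 is Day 85 (SAP Table 3-1). Visits have a ±3-day window (Protocol 6.3).
- Exposure = (last dose date − first dose date + 1), in weeks (SAP 4.2.1).
- Window end = end of GS-9992 + 30 days (SAP 7.1.5.1 and 7.2.3.1).
- Planned sizes are about 30 in each of Groups 1, 3 and 5, and about 20 in Group 4 (SAP 1.2).

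**The plan's own figures**
- 12 × 7 = 84 days, and 84 + 30 = Day 114, the Group 2 limit. This matches.
- 2 × 84 = 168 units for Groups 1, 3 and 5, and 84 for Group 4 (SAP 4.2.2.1). These match.

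**The fallback read literally, for a subject on TAF or NUC to Week 48**
- Imputed last GS-9992 day: 337 (334 to 340 with the visit window).
- Exposure: 337/7 = 48.1 weeks (47.7 to 48.6), against 84/7 = 12.0.
- Window end: 337 + 30 = Day 367 (364 to 370), against Day 114. The ratio is 367/114 = 3.2.

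**Effect of one such subject on a group mean**
- Excess: (337 − 84)/7 = 36.1 weeks.
- n = 30: 36.1/30 = 1.2 weeks, so the mean goes from 12.0 to 13.2.
- n = 20 (Group 4): 36.1/20 = 1.8 weeks, so the mean goes from 12.0 to 13.8.

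**If TAF or NUC stops earlier**
- Near Week 24 (Day 169): 169/7 = 24.1 weeks, window to Day 199.
- Near Week 36 (Day 253): 253/7 = 36.1 weeks, window to Day 283.

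**If the Week 12 visit is used instead**
- Day 85 ± 3 gives 82/7 = 11.7 to 88/7 = 12.6 weeks, and a window ending on Days 112 to 118, in line with Group 2.

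**What does not move**
- The Week 12 HBsAg endpoint is placed by study day from first dose (SAP 3.8.1 and Table 3-1).
- GS-9992 adherence uses unit counts over a fixed total (4.2.2.1).
- The GS-9992 cumulative exposure categories stop at Week 12 (4.2.1), so they cannot show 48 weeks.

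**The case against.** The strongest objection is textual. SAP 3.8.2 sorts data into on-treatment and posttreatment; it does not define an on-treatment period. The fallback follows a sentence about individual drugs, and 4.2.1 treats GS-9992 and TAF separately, so a programmer might take the period to be the one for that drug. This stands to the extent that the Week 48 result is possible rather than certain. It does not remove the problem: the SAP never gives the drug-specific reading, and that reading is circular, since a GS-9992 period cannot be closed without the missing date. SAP 7.2.2 also leans the other way, taking the last on-treatment value from the last dose of any drug, NUC included.

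The second objection is rarity. Drug start and end dates are required source data (Protocol 9.1.5), GS-9992 accountability is scheduled through Week 12 (Protocol Appendix 2), monitors raise queries (9.1.6), and both analyses wait for cleaned data (SAP 2.1 and 2.2). This stands; no document shows a missing stop date.

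Third, the damage is limited and traceable. A median would barely move, a 48-week value for a 12-week drug is conspicuous, and AEs and drug administration are listed by subject. The error adds events to the GS-9992 tables and hides none. In Group 4, Protocol 7.3 requires non-serious AEs only to 30 days after the last study drug, and SAP 3.1.2 does not count the NUC as one. Late Group 4 carry-over may therefore be mainly SAEs and laboratory values, although the schedule lists AE review at every visit. These points stand as limits on size. SAP 3.6.2 keeps outliers in the analysis, so noticing the value would not by itself correct it.

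A reader might infer that the primary safety tables are compromised. The documents do not support that: it would need affected subjects, and none is shown.

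**Conclusion.** The point holds as a minor flaw in a stated rule. On the only on-treatment definition given, a subject in Groups 1, 3, 4 or 5 with an unrecovered GS-9992 stop date could be assigned about 48.1 weeks of GS-9992 and a 12 Week Regimen AE and laboratory window to about Day 367 instead of about Day 114. These figures assume that 3.8.2 governs the fallback and that the subject stays on TAF or NUC to Week 48; the inflation is smaller if TAF or NUC ends sooner. The shifts of 1.2 and 1.8 weeks in mean exposure are for one affected subject among 30 or 20 who otherwise have 12.0 weeks. How many subjects are affected is unknown, and it may be none.

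**What to change.** Make the imputation drug-specific in SAP 3.8.1 and 4.2.1. For GS-9992, in this order:

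1. Use any recorded GS-9992 end date, even if its record is not flagged as permanently withdrawn.
2. Otherwise use the latest visit, laboratory or vital-signs date on or before the last GS-9992 accountability or bottle-return date.
3. If there is none, use the Week 12 visit date, or nominal Day 85 if that visit was missed.

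Do not truncate when accountability or administration records show later GS-9992 dosing. A flat cap at Week 12 would be simpler, but the protocol allows study drug to be withheld (7.6.2) and Group 5 dosing to be held and reinstated (6.11), and it does not say whether held doses are made up. If dosing did run later, a cap would shorten the safety window and lose events.

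Keep the current rule for TAF. The cost is a few lines of SAP text in two places and a small programming change. The accountability and visit dates are already scheduled for collection.

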#### **3.8.2. Analysis Visit Windows**

Subject visits might not occur on protocol-specified days. Therefore, for the purpose of analysis, observations will be assigned to analysis windows.

- For Groups 1-3 and 5

Data collected up to 3 days after the last dose date of GS-9992 or TAF, whichever comes last, will be considered as on-treatment data whereas data collected afterwards will be considered as posttreatment data.

- For Group 4

Data collected up to 3 days after the last dose date of GS-9992 or 3 days after the subjects have discontinued commercially available NUC(s), whichever comes last, will be considered as on-treatment data whereas data collected afterwards will be considered as posttreatment data.

On-treatment data will be mapped to the analysis windows defined in [Table 3-1](#), [Table 3-2](#), [Table 3-3](#) and [Table 3-4](#).

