#### **24 Week Treatment-Free Follow-up**

Subjects that meet any one of the following criteria will be followed for 24 weeks or until the initiation of alternative CHB therapy, whichever comes first:

- Subjects that discontinue all HBV therapy (e.g. GS-9992 and/or TAF or commercially available NUC), for any reason

- Subjects with HBsAg loss confirmed at least 12 weeks apart should discontinue all HBV therapy following confirmation

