**Table 3-2. Analysis Visit Windows for On-treatment Qualitative HBV Serology**

Analysis Visit	Nominal Study Day	Lower Limit	Upper Limit
Baseline	1	(none)	1
Week 12	85	2	127
Week 24	169	128	211
Week 36	253	212	295
Week 48	337	296	≥ 337

Note: For Group 4, subjects were treated with GS 9992 through Week 12 and continued on NUC afterwards.

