**Note:**

- a. For Group 4, subjects were treated with GS 9992 through Week 12 and continued on NUC afterwards.
- b. Creatinine clearance data are to be collected at screening, baseline, Week 12, Week 48 or early discontinuation. For purpose of analysis, baseline value will be the last available value prior to the first dose of any study drug. The Early Discontinuation value will be the last available value on or prior to the last dose date of any study drug + 3 days.

Posttreatment data will be mapped to the posttreatment follow-up (FU) analysis windows, which will be defined by FU Day.

- For Groups 1-3

FU Day = Assessment Date - Last Dose Date of GS-9992 or TAF (whichever comes last)

- For Group 4

FU Day = Assessment Date - Last Dose Date of GS-9992 or Date Subject Discontinued NUC (whichever comes last)

Posttreatment FU analysis windows are presented in [Table 3-5](#) and [Table 3-6](#).

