### **HBV Serology definitions:**

- **HBsAg loss:** HBsAg changing from positive at baseline to negative at any postbaseline visit.
- **Confirmed HBsAg loss:** HBsAg loss confirmed by any 2 consecutive results.
- **HBsAg loss reversion:** Any postbaseline HBsAg positive result following HBsAg loss.
- **HBsAb seroconversion:** HBsAb changing from negative or missing at baseline to positive at any postbaseline visit.
- **Confirmed HBsAb seroconversion:** HBsAb changing from negative or missing at baseline to positive at any postbaseline visit confirmed by any 2 consecutive results.
- **HBsAb seroreversion:** Any postbaseline HBsAb negative result following HBsAb seroconversion.

HBeAg-related terminology is defined similarly.

Lower LOQ (LLOQ) for HBV DNA is defined as 20 IU/mL. LLOQ for qHBsAg is defined as 0.05 IU/mL. LLOQ for qHBeAg is defined as 0.11 IU/mL.

Missing data will be treated as a non-event unless otherwise specified (eg, no HBsAg loss, no seroconversion, etc.)

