#### **6.2.2. Analysis Methods for Secondary Efficacy Endpoints**

The proportion of subjects with  $\geq 1 \log_{10}$  IU/mL decline in HBsAg from baseline at Week 12 will be analyzed on FAS similarly to the primary efficacy endpoint. Proportion point estimates and the 2-sided 95% exact CIs will be provided by HBeAg status (positive, negative) and overall for each treatment group. CIs of the proportion point estimates will be constructed based on the Clopper-Pearson method. In addition, the proportion differences (Group 1 - Group 2, Group 3 - Group 2, and Group 5 - Group 2) and the corresponding 2-sided 95% CIs will be reported. CIs of the proportion differences will be calculated by using stratum-adjusted MH proportions, stratified by HBeAg status (positive, negative).

A summary table will be provided for HBsAg-related serology results. The proportion of subjects who have ever had HBsAg loss, confirmed HBsAg loss, on-treatment HBsAg loss, posttreatment HBsAg loss (for subjects with positive HBsAg at the end of the on-treatment period), HBsAg loss with HBsAb seroconversion, HBsAg loss with HBsAb seroreversion, and HBsAg loss reversion with or without HBsAb seroconversion will be summarized by HBeAg status (positive, negative) and overall for each treatment group.

Additional summary tables may be provided for the following:

If  $\geq 3$  subjects achieved HBsAg loss,

- The proportion of subjects with HBsAg loss will be summarized by visit through Week 48;

If  $\geq 3$  subjects achieved HBsAg loss with HBsAb seroconversion,

- The proportion of subjects with HBsAb seroconversion will be summarized by visit through Week 48
- The proportion of subjects who have ever had HBsAg loss with HBsAb seroconversion, confirmed HBsAb seroconversion, on-treatment HBsAb seroconversion, posttreatment HBsAb seroconversion (for subjects with negative or missing HBsAb at the end of the on-treatment period) will be summarized.

For subjects in the FAS with baseline HBeAg status positive, similar summary tables will be provided for HBeAg-related serology results.

Summary statistics will be presented by HBeAg status (positive, negative) and overall for each treatment group for absolute values and change from baseline in HBV DNA ( $\log_{10}$  IU/mL) (Group 1- 3, and 5) and qHBsAg ( $\log_{10}$  IU/mL) by visit (Group 1- 5).

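### By-visit HBsAg and HBV DNA summaries at Week 48, and sometimes Week 36, leave out subjects who stopped therapy because they lost HBsAg

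*SAP*

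**What the plan says.** **Stopping rule.** Protocol section 3.2 (also the synopsis and SAP 1.2): "Subjects with HBsAg loss confirmed at least 12 weeks apart should discontinue all HBV therapy following confirmation". These subjects then enter 24 weeks of treatment-free follow-up (TFFU), cut short if they start other therapy.

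**Windows.** For Groups 1-3 and 5, SAP 3.8.2 says "Data collected up to 3 days after the last dose date of GS-9992 or TAF, whichever comes last, will be considered as on-treatment data". Group 4 has a parallel rule tied to stopping the NUC: "3 days after the subjects have discontinued commercially available NUC(s), whichever comes last, will be considered as on-treatment data". The Week 1 to Week 48 windows take on-treatment data only: "On-treatment data will be mapped to the analysis windows defined in" Tables 3-1 to 3-4, and Table 3-2 is headed "Analysis Visit Windows for On-treatment Qualitative HBV Serology". After that, "Posttreatment data will be mapped to the posttreatment follow-up (FU) analysis windows, which will be defined by FU Day". No exception is made for subjects who stop because they responded.

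**Outputs.** SAP 6.2.1 lists change from baseline in quantitative HBsAg (all groups) and HBV DNA (Groups 1-3 and 5) as secondary endpoints. SAP 6.2.2 summarizes and plots both by visit, and SAP 3.6.1 does not impute. HBsAg loss is mainly reported cumulatively. An optional extra table applies if at least 3 subjects lose HBsAg: "The proportion of subjects with HBsAg loss will be summarized by visit through Week 48".

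**Missing data.** SAP 6.2.1 says "Missing data will be treated as a non-event unless otherwise specified". SAP 6.2.2 calls for a missing-excluded analysis apart from borderline results. Protocol 8.3 sets missing equal to failure for categorical secondary endpoints.

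**The concern.** The trial has a stop-on-success rule, and the windows treat stopping as the end of usable by-visit data. The subjects with the largest HBsAg declines are therefore the ones whose later values leave the Week 36 and Week 48 rows, even though samples are taken at about those times. This missingness depends on the outcome. The better a regimen does at producing confirmed loss, the more its tabulated late mean change understates it.

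The objectives cover the period after GS-9992 stops through 48 weeks, and SAP 2.1.2 takes data to the end of the 48-week study period. The by-visit tables are where a reader would look for the late course of HBsAg.

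**Working it through.** There is no sample-size or power figure to reproduce. The check traces subjects through the SAP's windows.

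**Inputs**
- Nominal day = 7 × week + 1, giving Days 85, 169, 253 and 337 for Weeks 12, 24, 36 and 48. These match Tables 3-1 and 3-2.
- Windows: Week 36 is Days 212-295; Week 48 is Day 296 onward.
- FU Day = assessment date − last dose date (SAP 3.8.2).
- Scheduled qualitative serology: Weeks 12, 24, 36 and 48 (protocol 6.3), so the earliest scheduled confirmation is Week 24.
- Assumption: last dose falls 0 to 28 days after the confirming visit.

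**Trace**

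| First negative, confirmed | Last on-treatment day | Day 253 (Week 36) | Day 337 (Week 48) |
|---|---|---|---|
| Week 12, Week 24 (Day 169) | 172 to 200 | FU Day 84 to 56 (FU Week 12 or 8) | FU Day 168 to 140 (FU Week 24 or 20) |
| Week 24, Week 36 (Day 253) | 256 to 284 | on treatment | FU Day 84 to 56 (FU Week 12 or 8) |
| Week 36, Week 48 (Day 337) | 340 to 368 | on treatment | on treatment |

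In the first row Day 200 is before Day 212, so no on-treatment record can fill Week 36. In the second row Day 284 is before Day 296, so none can fill Week 48. The third row loses nothing.

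**Week 12.** Even a loss seen on Day 8 could not be confirmed before Day 8 + 84 = 92, after nominal Day 85. The primary endpoint is not touched.

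**How many subjects.** Protocol 1.3.2 gives HBsAg loss on TAF as 0/285 and 4/581, that is 4/581 = 0.69%, or 4/866 = 0.46% pooled. The GS-9992 rate is not given, so 1%, 2% and 5% are assumptions. With n = 120, expected losses = np and P(≥3) = 1 − Σ(j=0..2) C(120,j) p^j (1−p)^(120−j):

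| Rate | Expected losses | P(≥3) |
|---|---|---|
| 0.46% | 0.55 | 1.9% |
| 0.69% | 0.83 | 5.1% |
| 1% | 1.2 | 12% |
| 2% | 2.4 | 43% |
| 5% | 6.0 | 94% |

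These are upper bounds for the exposed subjects, since only losses first seen by Week 24 leave a gap.

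**Effect on the mean.** For k responders of 30, mean = [(30 − k) × m0 + k × mR] / 30. Assume m0 = −0.2 log10 in the others and mR = −2 to −4:
- k = 1: (29 × −0.2 − 2)/30 = −0.26, to (29 × −0.2 − 4)/30 = −0.33
- k = 3: (27 × −0.2 − 6)/30 = −0.38, to (27 × −0.2 − 12)/30 = −0.58
- responders dropped: −0.20

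A larger fall is possible. The 25 mg cohort's mean baselines (4.38 and 3.18 log10), mixed 60/40, give 0.6 × 4.38 + 0.4 × 3.18 = 3.90. A result below 0.05 is set to 0.04 IU/mL (SAP 3.7), and log10(0.04) = −1.40, so the change is −5.30. With −0.30 assumed in the others and k = 3, the mean is (3 × −5.30 + 27 × −0.30)/30 = −0.80, against −0.30 with responders dropped.

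**By-visit loss table.** If it shows status at each visit and 3 of 30 stopped after Week 24 and stayed negative, Week 48 reads 0/30 (non-event) or 0/27 (excluded) instead of 3/30. The SAP does not say whether the table is visit status or cumulative.

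**The case against.** A reader might infer that the best responders count as failures for the 48-week HBsAg-loss endpoint, or that their data vanish. The documents do not support either. Loss is defined as a negative result at any postbaseline visit, and the one unconditional table reports whether loss ever occurred, with confirmed, on-treatment, posttreatment and reversion rows (SAP 6.2.1 and 6.2.2). A subject who stops for confirmed loss already has on-treatment negatives and is an event: 3/30 under either windowing. A figure of 0% against 10% is one reading of an optional table, not the endpoint result. For Groups 1-4 the later records reappear in the follow-up windows.

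Other arguments carry weight:
- The endpoints for Groups 1-3 and 5 in the protocol, and for all groups in the SAP, refer to 48 weeks of treatment. On-treatment windows fit that wording, and keeping HBV DNA after NUC withdrawal apart is defensible. But the objectives and SAP 2.1.2 cover the whole 48-week period, and neither document says the late means condition on not having responded.
- Loss may be rare. The only GS-9992 HBsAg declines given are maximal falls of 0.52 to 1.01 log10 in 5 of 16 subjects at 25 mg (protocol 1.2.2), far short of loss. Three of 30 is only an illustration.
- The SAP also reports medians. In the stylized case above, with the other 27 all equal, the median does not move.
- Stopping is not certain. Protocol 3.2 uses should, while the list in 6.11 uses may. The two passages need reconciling.
- The study is exploratory and tests no hypothesis.

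These points limit the size of the problem. They do not remove it: one responder is enough to shift a mean over 30 subjects.

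**Conclusion.** The point holds for the by-visit outputs only. Quantitative HBsAg and HBV DNA values, changes and plots at Week 48, and at Week 36 for subjects first negative by Week 12, omit subjects who stopped because they responded. So does the optional by-visit loss table if it shows visit status. For quantitative HBsAg this attenuates the mean change in a listed secondary endpoint. The effect on HBV DNA was not quantified.

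The size depends on how many subjects lose HBsAg by Week 24: nil if none do, and a shift from −0.20 to between −0.26 and −0.33 for one responder in 30 on the milder assumptions. The trace rests on scheduled serology and a lag of at most 28 days to last dose; the responder counts and declines are assumptions. It is worth correcting before the final analysis, and it does not threaten the primary result.

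**What to change.** Amend SAP 3.8.2:

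1. For HBsAg and HBeAg serology, quantitative HBsAg and HBV DNA in the 48-week efficacy tables, window all records through Week 48 by study day from first dose, on or off study drug. Apply this to every subject who stopped for any reason, using records before any alternative CHB therapy. Restoring only responders' records would favor the drug.
2. Show the number off treatment at each visit. Keep the on-treatment version, and keep the FU-week mapping for the TFFU tables.
3. Do not impute success for missing records. State one missing-data rule for the by-visit serology tables, reconciling SAP 6.2.1 and 6.2.2 with protocol 8.3, and say whether those tables show visit status or cumulative loss.
4. State an upper limit for the Week 48 window, which Tables 3-1 and 3-2 leave open. Otherwise later follow-up records enter it, and SAP 3.8.3 picks the most favorable serology value in a window.
5. Add Group 5 to the FU Day definition, which names only Groups 1-3 and Group 4. As written, Group 5 posttreatment records have no defined FU Day.

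**Cost.** SAP wording and programming, with no new visits or samples. After a Week 24 stop, FU Weeks 12 and 24 already include serology (protocol 6.5). They fall at Days 169 + 84 = 253 and 169 + 168 = 337, or 28 days later (281 and 365) at the longest assumed lag, inside the current Week 36 and Week 48 windows.

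**Downside.** Week 36 and Week 48 rows will mix on-drug and off-drug values, including HBV DNA after NUC withdrawal; the retained on-treatment version separates them. Subjects who stop well before Week 24 finish follow-up before Week 48 (a Week 8 stop ends at 8 + 24 = 32 weeks) and stay missing there, so the counts at each visit should be read with the means.
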